3.1.2 Study Intervention Phase

All patients will have blood collected prior to treatment for storage. Archival tumor tissue samples, if available, will also be collected and stored. If considered safe and feasible, a tumor biopsy will be obtained prior to the first dose of rucaparib.

During the treatment phase (continuous 28 day cycles), patients will be monitored for safety and efficacy. Assessments during the treatment phase will include AEs, ECOG performance status, concomitant medications and procedures, physical examination, vital signs and weight measurements, hematology and serum chemistry, serum or urine pregnancy (per investigator discretion) for women of childbearing potential, CA 19-9 measurement, blood samples for circulating tumor material analyses and study drug administration and accountability. Patients will be assessed for disease status per RECIST v1.1 after every 2nd cycle of treatment, and then every 3rd cycle for patients who have been on the study drug for at least 2 years. Patients will continue to receive rucaparib until disease progression or other reason for treatment discontinuation.

Patients will be monitored continuously for safety. The Data and Safety Monitoring Committee (DMSC) of the University of Pennsylvania Clinical Trials Scientific Review and Monitoring Committee (CTSRMC) will evaluate safety and efficacy in compliance with a charter.

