4.3 Patients or Partners of Patients with Reproductive Potential

Pregnancy is an exclusion criterion for study patients. Female study patients of childbearing potential, must not be considering getting pregnant during the study until 6 months following the last dose of rucaparib. Female partners of childbearing potential of study patients must not be considering getting pregnant during the study until 3 months following the last dose of rucaparib.

A woman is considered to be of childbearing potential unless 1 of the following applies:

- She is considered to be permanently sterile. Permanent sterilization methods include hysterectomy, bilateral salpingectomy, and bilateral oophorectomy.
- She is postmenopausal, defined as no menses for 12 months without an alternative medical cause. A high follicle-stimulating hormone (FSH) level consistently in the postmenopausal range (30 mIU/mL or higher) may be used to confirm a postmenopausal state in women not using hormonal contraception or hormonal replacement therapy; however, in the absence of 12 months of amenorrhea, a single FSH measurement is insufficient to confirm a postmenopausal state.

Female patients of childbearing potential must have a negative serum pregnancy test result less than 3 days prior to administration of the first dose of rucaparib. In addition, a serum pregnancy test must be performed < 3 days prior to Day 1 of every cycle from Cycle 2 and beyond. Treatment should be discontinued immediately in any woman found to have a positive pregnancy test while taking rucaparib. A serum pregnancy test will also be performed at the End-of-Treatment Visit.

Female study patients of reproductive potential must practice total abstinence or use a highly effective method of contraception (failure rate < 1% per year) during treatment and for 6 months following the last dose of rucaparib. Female partners of reproductive potential and their male partners must practice total abstinence or use a highly effective method of contraception (failure rate < 1% per year) during treatment and for 3 months following the last dose of rucaparib. The following are allowable only:

- Ongoing use of progesterone-only injectable or implantable contraceptives (e.g., Depo Provera, Implanon, Nexplanon)

CONFIDENTIAL

This material is the property of the University of Pennsylvania.

- Placement of an intrauterine device or intrauterine system
- Bilateral tubal occlusion

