5.2 Intervention Regimen

Patients will take 600mg rucaparib orally BID with at least 8oz (240mL) of room temperature water starting on Day 1. Rucaparib may be taken on an empty stomach or with food. Tablets should be swallowed whole without crushing or chewing. Patients should take rucaparib doses as close to 12 hours apart as possible, preferably at the same times every day. If a patient misses a dose (i.e. does not take it within 4 hours of the scheduled time), they should skip the missed dose and resume taking rucaparib with their next scheduled dose. Missed or vomited doses should not be made up.

A sufficient number of tablets will be provided to the patient to last until the next scheduled visit. Patients will be instructed to record daily doses taken or not taken in the dosing diary, and will be instructed to bring

CONFIDENTIAL

their rucaparib tablets, all containers (empty, partially used, and/or unopened) and dosing diary to the next scheduled visit for reconciliation by the study personnel. Patients will take rucaparib BID for continuous 28-day cycles until disease progression as assessed by the investigator, or other reason for discontinuation. Treatment interruption and/or dose reductions are permitted in the event of unacceptable toxicity.

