6 STUDY PROCEDURES

6.1 Schedule of Assessment

All procedures and assessments are to be completed within ± 3 days of the scheduled time point.

Schedule of Assessments						
Procedure ^a	Screening Phase	Treatment Phase			Post-Treatment Phase	
	Day -28 to Day -1 (unless otherwise specified)	Cycles 1 & 2		Cycles 3+ ^{x & y}		
		Day 1 ^b	Day 15	Day 1	End of Treatment	28-day FU (28 \pm 3 days after last dose)
Informed Consent	X					
Demographics and Med/Onc History ^c	X					
Physical Exam, Height ^d , Weight	X	X		X	X	
Vital Signs ^f	X	X ^e		X ^e	X	
Adverse Events	X	X	X	X	X	X
Prior/Concomitant Medications and Procedures	X	X	X	X	X	
12-lead-ECG ^g	X				X	
Hematology ^h	X ⁱ	X	X	X ^x	X	
Serum Chemistry ^j	X ⁱ	X	X	X	X	
CA 19-9 measurement		X		X	X	
Coags if undergoing a tumor biopsy ^u	X				X	
Serum/Urine Pregnancy Test ^k (WOCBP only)	X	X		X	X	
Urinalysis ^l	X					
Disease Assessment/Tumor Scans ^m	X			X ⁿ	(X) ^o	(X) ^p
	Screening Phase	Treatment Phase				
	Day -28 to Day -1 (unless otherwise specified)	Cycles 1 & 2		Cycles 3+ x & y		
		Day 1	Day 15	Day 1		
Archival Tumor Tissue (if available)		X				
Tumor Tissue Biopsy (if safe/feasible) ^r	X				X ^w	
Research sample ^t		X		X	X	

CONFIDENTIAL

Schedule of Assessments							
Rucaparib Dispensation, Administration, Accountability		X		X	X		
Survival Status							X ^s

ALP = alkaline phosphatase, ALT = alanine transaminase, ANC = absolute neutrophil count, AST = aspartate transaminase, BUN = blood urea nitrogen, CR = complete response, CT = computed tomography, ECG = electrocardiogram, hrs = hours, MRI = magnetic resonance imaging, PET = positron emission tomography, PK = pharmacokinetics, PR = partial response, SAE = serious adverse event, WBC = white blood cell, WOCBP = women of childbearing potential

^a = Treatment cycles are 28 days except for patients who reach C11D1 and are clinically stable as per the investigator may be extended to a 56-day cycle. Unless otherwise specified, all assessments are to be completed within ± 3 days of scheduled time point. Delay of treatment schedule up to 10 days, as allowed by the protocol, is permitted at the discretion of the treating Investigator with approval of the PI (e.g. toxicity, weather, vacation). In addition, on a case by case basis the cycle length maybe extended to allow for planned vacations or emergency situations if deemed clinically stable by the PI.

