^b = Any procedures required on Day 1 of Cycle 1 may be omitted if completed ≤ 3 days earlier during the screening period.

^c = Patient's medical record must include prior treatments received, dates of administration, date of progression, and radiology and/or medical report(s) to support assessment of disease progression, and, if applicable, intolerable toxicity to chemotherapy. Detailed BRCA1/2 test results are also required prior to enrollment.

^d = Height at screening only.

^e = Vital signs (blood pressure, pulse, and temperature) to be taken pre-dose on clinic visit days.

^f = AEs are recorded from the time of signing informed consent through 28 days after last dose of rucaparib. Ongoing SAEs will be followed to resolution or until SAE stabilizes.

^g = Heart rate, PR, QRS, QT, QTc and rhythm. Investigator to review results and assess as normal or abnormal (clinically significant or not clinically significant). ECGs to be repeated as clinically indicated.

^h = Includes CBC with differential which includes: hemoglobin, hematocrit, WBC and differential (with ANC) and platelet count. Blood will be analyzed by a local laboratory.

ⁱ = to be performed ≤ 7 days prior to the first dose of rucaparib.

^j = includes total protein, albumin, creatinine or estimated GFR using Cockcroft Gault formula, BUN, total bilirubin, ALP, ALT, AST, glucose, sodium, potassium, chloride, CO₂, calcium and phosphorous. Blood will be analyzed by a local laboratory.

^k = Women of childbearing potential must have a negative serum pregnancy test result ≤ 3 days prior to the first dose of rucaparib. A serum or urine pregnancy test (investigator's discretion) must be performed ≤ 3 days prior to Day 1 of every cycle during the treatment phase. A serum pregnancy test must be performed at the End of Treatment visit.

^l = includes dipstick for protein, glucose, blood, pH and ketones. If dipstick findings are abnormal based on investigator's assessment, microscopic evaluation should be performed.

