^w= A biopsy will be obtained at progression if deemed safe and feasible. For patients some patients this will not be considered end of treatment as they may be permitted to remain on treatment past progression ^x= Following C11D1 of treatment, patients who are deemed to be clinically stable as per the investigator may have office visits and blood work at every odd cycle only. Subjects will be required to have monthly hematology labs (complete blood counts). A cycle will then be 56 days.

^y= Following C24D1 of treatment, patients who are deemed to be clinically stable as per the investigator may have office visits, including imaging and clinical assessments, Q12 weeks instead of Q8 weeks. A cycle will then be 84 days. Clinical labs should still be obtained once per month.

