7.7 Clinical Laboratory Evaluations

Certified local laboratories will perform study-related clinical laboratory tests according to institutional procedures, and the results will be reviewed by the investigator. The panels of laboratory tests to be performed are shown below:

Hematology: Hemoglobin, hematocrit, WBC and differential (with ANC), and platelet count at Screening, during treatment, and at the End of Treatment visit. Screening hematology results must be reviewed by the investigator prior to the start of treatment with rucaparib. During the treatment phase, results must be evaluated by the investigator and acted upon, as appropriate, within 24 hrs of receipt.

Clinical Chemistry: Total protein, albumin, creatinine or estimated GFR using the Cockcroft Gault formula, BUN or urea, total bilirubin, alkaline phosphatase (ALP), ALT, AST, glucose, sodium, potassium, chloride, CO₂, calcium, and phosphorus at Screening, during treatment, and at the End of Treatment visit. Screening clinical chemistry results must be reviewed by the Investigator prior to the start of treatment with rucaparib. During the treatment phase, results must be evaluated by the investigator and acted upon, as appropriate, within 24 hrs of receipt.

Urinalysis: Performed on freshly voided clean sample by dipstick for protein, glucose, blood, pH, and ketones per the schedule of evaluations. If dipstick findings are abnormal, then a microscopic evaluation will be performed to assess the abnormal findings. Urinalysis will be performed at screening only.

Serum/Urine Pregnancy: For women of childbearing potential only. Serum pregnancy test is to be performed ≤3 days prior to first dose of rucaparib and at the End of Treatment visit. Serum or urine pregnancy test (per investigator's discretion) is to be performed ≤3 days prior to the start of every cycle during the treatment phase.

Laboratory reports will be reviewed by the investigator or delegated physician who will then comment on out-of-range parameters and assess clinical significance. Clinically significant abnormalities and associated panel results, as well as results of any additional tests performed as follow-up to the

CONFIDENTIAL

abnormalities, will be documented on the eCRF as an AE. Refer to Section 9.4 for guidelines on reporting of abnormal laboratory values as AEs.)

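### On-treatment pregnancy tests are set per cycle with no calendar interval, so the 56-day cycle allowed from C11D1 lets a compliant site test every 56 days instead of every 28 (low-priority safety clarification)

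*Combined protocol and SAP*

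**What the plan says.** Section 4.3 requires that "a serum pregnancy test must be performed < 3 days prior to Day 1 of every cycle from Cycle 2 and beyond". Schedule footnote k says "A serum or urine pregnancy test (investigator's discretion) must be performed" within 3 days before Day 1 of each cycle. Section 7.7 agrees: "Serum or urine pregnancy test (per investigator's discretion) is to be performed ≤3 days prior to the start of every cycle". Sections 6.3.1 (Cycles 1 and 2) and 6.1.3 (Cycles 3 and beyond) are also per cycle. None gives a number of days. The only other scheduled tests are a serum test before the first dose and one at End of Treatment.

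The cycle length is not fixed. Footnote a carves out an exception to 28 days: "patients who reach C11D1 and are clinically stable as per the investigator may be extended to a 56-day cycle". Footnote x moves visits and blood work to odd cycles after C11D1 and adds: "Subjects will be required to have monthly hematology labs (complete blood counts). A cycle will then be 56 days". Section 6.4 gives the same odd-cycle option and names only monthly hematology between visits. Later, footnote y (from C24D1) allows an 84-day cycle with monthly clinical labs, while Section 6.5 (from C23D1) names only monthly hematology.

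Other sections keep to 28 days. Section 3.1.2 has "During the treatment phase (continuous 28 day cycles), patients will be monitored for safety and efficacy", and Section 5.2 has "Patients will take rucaparib BID for continuous 28-day cycles until disease progression".

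**The concern.** A safety test defined per cycle becomes less frequent when the cycle is lengthened. Through Cycle 10, per cycle means nominally every 28 days. If the cycle then becomes 56 days, one test per 56 days meets every rule while twice-daily dosing continues. The reduced schedule keeps the blood count monthly but does not mention the pregnancy test.

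What is at stake is the time to detection. Section 4.3 stops treatment on a positive test. Section 9.7 stops dosing if a patient becomes pregnant, and patients are told to report a pregnancy. The stop in 9.7 and the reporting duty act only once a pregnancy is known; the scheduled test is what finds one not yet recognised. Section 1.3 reports a clastogenic result in vitro that points to possible genotoxicity in humans.

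**Working it through.** The plan states no figure for the testing interval, so there is none to reproduce. The check compares the texts and then sizes the gap.

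**Two readings from C11D1**

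- *56-day cycle (footnotes a and x).* One test per 56 days satisfies every per-cycle rule. Nothing requires a pregnancy test between Day 1 visits.
- *28-day numbering (3.1.2, 5.2, 5.6, 6.1.3, 6.4).* A test is due every 28 days. At even cycles there is no office visit, Section 6.4 lets the patient omit that blood work, and the test is not listed with the monthly hematology draw that does take place.

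**Size of the gap** (interval L days; doses = 2L; tests per year = 365.25/L; mean wait from a random time point to the next scheduled test = L/2)

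| L | Twice-daily doses between tests | Tests per year | Mean wait |
|---|---|---|---|
| 28 | 56 | 13.0 | 14 days |
| 56 | 112 | 6.5 | 28 days |

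These are nominal. Footnote a has a ±3-day window and adds: "Delay of treatment schedule up to 10 days, as allowed by the protocol, is permitted at the discretion of the treating Investigator".

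**How many women (illustrative)**

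1. C11D1 falls after 10 × 28 = 280 days.
2. The plan assumes exponential PFS with PFS6 of 44% (null) or 60% (alternative) and 42 patients. The number progression-free at day d is 42 × exp[ln(PFS6)/6 × d/30.4375].
3. At d = 280 this gives 11.9 (44%) and 19.2 (60%).
4. The share of childbearing potential is not in the documents. Assuming 5% to 20%, the range is 11.9 × 0.05 = 0.6 to 19.2 × 0.20 = 3.8 women.
5. With no administrative cut-off, person-years after C11D1 are the number at C11D1 divided by the yearly hazard, −ln(PFS6)/6 × 12. That is 11.9/1.642 = 7.3 and 19.2/1.022 = 18.8.
6. Woman-years run from 7.3 × 0.05 = 0.4 to 18.8 × 0.20 = 3.8.
7. At the contraceptive failure rate of under 1% per year in Section 4.3, that is fewer than about 0.004 to 0.04 pregnancies in the whole trial.

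**84-day stage**

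The start depends on which section and which numbering apply.

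| Start | 28-day numbering throughout | 56-day cycles from C11 |
|---|---|---|
| C23D1 (6.5) | 22 × 28 = day 616: 2.6 to 7.5 patients | 280 + 12 × 56 = day 952: 0.6 to 2.9 patients |
| C24D1 (footnote y) | 23 × 28 = day 644: 2.3 to 6.9 patients | 280 + 13 × 56 = day 1008: 0.5 to 2.5 patients |

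With the same 5% to 20% share, this is at most about 1.5 women.

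**The case against.** The strongest reply is that 28-day numbering is the coherent reading. If each numbered cycle were 56 days and visits fell at odd cycles only, visits would be 2 × 56 = 112 days apart, and so would the scans that footnote n ties to odd cycles. Yet Section 6.4 leaves the imaging schedule unchanged, and footnote y and Section 6.5 describe the preceding interval as 8 weeks. Section 3.1.2 moves to every third cycle after two years, which matches the later 12-week interval only if a cycle is 28 days. Section 5.6 supplies 28 days of drug per cycle, and Section 6.1.3 dispenses for two cycles at a time. On this view 56 days describes the visit interval, and Section 4.3 already requires 28-day testing. This stands as evidence of intent. It does not remove the express words of footnotes a and x, nor does it give the even-cycle test a named place in the schedule.

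The second reply is that the benefit is tiny. An extra test prevents no pregnancy; it brings detection forward by 28 − 14 = 14 days on average. At most that is 0.04 × 14, about half a day of expected exposure across the trial. Contraception is the main control and does not change at C11. This also stands, and it sets the priority.

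A reader might infer that the protocol sets a 56-day interval, or that the gap plainly reaches 84 days. Neither is supported. The first is permitted by one of two readings. The second is unclear, because footnote y keeps monthly clinical labs and Section 7.7 lists pregnancy testing among the clinical laboratory evaluations.

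**Conclusion.** The point holds as an ambiguity with a permitted consequence. Because testing is per cycle and the cycle may be called 56 days from C11D1, a compliant site may test at half the frequency that the trial uses through Cycle 10. If 28-day numbering was meant, the even-cycle test is due without a scheduled visit or a listed lab. The 84-day stage is unclear.

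The expected impact is very small, roughly under 0.04 pregnancies. That rests on exponential PFS, the assumed 5% to 20% childbearing share, contraceptive failure below 1% per year and no administrative cut-off. A reader might take the 11.9 to 19.2 patients as an upper bound, but they are only illustrative. Section 5.2.4 allows treatment beyond progression, and Section 8 replaces non-evaluable patients, so more than 42 may be dosed. In the other direction, not every progression-free patient will be on drug, stable and on the reduced schedule. PFS6 and power are unaffected. The clarification is worth making because it costs almost nothing, but it is low priority.

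**What to change.** - In Section 4.3 and footnote k, keep the 3-day windows and the serum tests before the first dose and at End of Treatment. After the per-cycle requirement add: *and at least every 28 days while on rucaparib, regardless of cycle length or visit schedule*.
- In footnotes x and y and in Sections 6.4 and 6.5, add *pregnancy test (WOCBP)* to the monthly labs. Sections 6.4 and 6.5 already have a study investigator review the monthly hematology labs and allow them to be done locally.
- As a separate and explicit decision, reconcile Section 4.3, which asks for serum every cycle, with footnote k and Sections 6.1.3 and 7.7, which allow serum or urine. The interval edit should not settle this silently in the looser direction.

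The cost is a wording amendment plus one extra low-cost test per 56-day interval (up to two per 84-day interval) for a few women. Over 336 days that means 12 tests, against 6 with 56-day cycles or 4 with 84-day cycles. No extra visit is needed, because the monthly draw is already required.

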4.4 Total Number of Subjects and Sites

42 subjects will be enrolled at the University of Pennsylvania.

4.5 Vulnerable Populations:

Children, pregnant women, fetuses, neonates, or prisoners are not included in this research study.

5 Study Intervention (Study drug, device, biologic, vaccine, food etc.)

Oral rucaparib

5.1 Description

Rucaparib camsylate (also known as CO-338; previously known as PF-01367338-BW and AG-014447) is an oral formulation with a molecular weight of 555.67 Daltons. Rucaparib tablets for oral administration will be supplied to the study site by Clovis Pharmaceuticals Inc. A brief description of the investigational product is provided below.

Drug Name:	Rucaparib
INN:	Rucaparib
Formulation:	Tablet; film coated 200 mg – blue, round, embossed with C2 300 mg – yellow, oval, embossed with C3
How Supplied:	200 and/or 300 mg strength (based on free base) in high-density polyethylene bottles or equivalent with child-resistant caps. Patients may receive 1 or more strengths.
Storage Conditions:	Store at room temperature, with no special storage conditions. (Can remove temps all places as well)

5.2 Intervention Regimen

Patients will take 600mg rucaparib orally BID with at least 8oz (240mL) of room temperature water starting on Day 1. Rucaparib may be taken on an empty stomach or with food. Tablets should be swallowed whole without crushing or chewing. Patients should take rucaparib doses as close to 12 hours apart as possible, preferably at the same times every day. If a patient misses a dose (i.e. does not take it within 4 hours of the scheduled time), they should skip the missed dose and resume taking rucaparib with their next scheduled dose. Missed or vomited doses should not be made up.

A sufficient number of tablets will be provided to the patient to last until the next scheduled visit. Patients will be instructed to record daily doses taken or not taken in the dosing diary, and will be instructed to bring

CONFIDENTIAL

their rucaparib tablets, all containers (empty, partially used, and/or unopened) and dosing diary to the next scheduled visit for reconciliation by the study personnel. Patients will take rucaparib BID for continuous 28-day cycles until disease progression as assessed by the investigator, or other reason for discontinuation. Treatment interruption and/or dose reductions are permitted in the event of unacceptable toxicity.

